The study will enroll children of either gender, age from 7 to 12 years old with diagnosis of attention deficit/hyperactivity disorder (ADHD) verified by Diagnostic and Statistical Manual of Mental Disorders, Fifth Edition, American Psychiatric Association» [DSM-V].

After signing patient information sheet and informed consent form by the patient's parent/adoptive parent collection of complaints, examination of the children, filling Attention Deficit Hyperactivity Disorder-Rating Scale-V [ADHD-RS-V] scale by the parent/adoptive parent (for children aged 7-10 years old, for teenagers aged 11-12 years old) will be performed, concomitant therapy will be recorded and laboratory tests will be carried out.

The study will enroll children with a total score ADHD-RS-V ≥ 22 .

If the inclusion criteria were met and there were no exclusion criteria (Day 1), the patient is randomized to one of the two groups: group 1 will receive Prospekta at 1 tablets twice daily; group 2 will receive Placebo using the study drug dosing regimen.

Treatment period is 8 weeks, the main stages of the examination (collection of complaints, registration of objective examination data, re-filling of the ADHD-RS-V scale by the parent/adoptive parent) are made at Visit 1 (Day 1), then 4 weeks later (Visit 2) and 8 weeks later (Visit 3). Each visit to the investigational site is made by the patient is accompanied by his/her parent/adoptive parent. Two weeks later (Visit 1.1, week 2 \pm 3 days) after randomization and initiation of the study therapy and between Visits 2 and 3 (Visits 2.2, week 6 \pm 3 days) the investigator checks the patient's clinical condition during «phone visits»: based on the collection of complaints, control of prescribed therapy, evaluates the safety of treatment. At Visit 2 (week 4 \pm 3 days) and Visit 3 (week 8 \pm 3 days) the investigator collects complaints, registers objective examination data, controls re-filling by the patient's parent/adoptive parent of the ADHD-RS-V scale, the prescribed and concomitant therapy, assesses the safety of the treatment and the degree of adherence of the patient to the study therapy (compliance). Additionally, at Visit 3 the investigator completes the Clinical Global Impression Efficacy Index [CGI-EI] scale and collect samples for laboratory testing. The patient stops taking the study drug.

The total duration of the observation period is 8 weeks.

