7. Any other co-morbidity which, in the opinion of the investigator, may affect patient participation in the clinical trial.
8. Patients allergic to/intolerant of any components of the study treatment.
9. Hereditary lactose intolerance, malabsorption due to lactose intolerance including congenital or acquired lactase (or other disaccharide) deficiency, galactosemia.
10. Patients whose parents/adoptive parents will not fulfill the requirements during the study or follow the order of administration of the study drug (SD) products, from the Investigator's point of view.
11. History of treatment noncompliance, mental diseases, alcoholism or drug abuse in parents/adoptive parents which, according to the investigator, will prevent from following the study procedures.
12. Administration of the products outlined in section "Prohibited concomitant therapy" within 1 month prior to enrollment.
13. Patients who have participated in other clinical trials in the past 3 months.
14. The patient's parent/adoptive parent is a study specialist of the center and is directly involved in the study, or is an immediate family member of the Investigator. Spouses, parents, children, or siblings, regardless of whether they are siblings or adopted are considered immediate family members.
15. The patient's parent/adoptive parent works at OOO "NPF "MATERIA MEDICA HOLDING", i.e. they are employees of the Company, temporary employees on a contract basis or appointed officials responsible for conduction of the study or their immediate family members.

Criteria for Withdrawal or Termination

1. Screening failure.
2. Parent's/adoptive parent's failure or unwillingness to comply with the protocol requirements.
3. Necessity in medications prohibited within the study.
4. An adverse event requiring discontinuation of the study drug.

5. Eligibility error.
6. Parent's/adoptive parent's wish to terminate the study early for any reason.
7. Enrollment of the subject into another clinical study.
8. Cases not specified by the protocol when, according to the investigator's opinion, further participation in the study harms the patient.
9. Pregnancy.
10. Unblinding.

Number of subjects

It is planned to include 366 subjects, which is expected to yield at least 292 (146 in Prospekta and Placebo groups) patients completing all protocol procedures.

Interim analysis

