¹ Sexually active teenagers - at the parent's/adoptive parent's disposal

Statistical Analyses

Samples

Total set includes all enrolled patients' parents/adoptive parents who have signed ICF. This sample will consider all adverse events (AEs) throughout the study, including those occurred prior to the study therapy.

The sample including all patients who received at least one dose of the study drug to be used for ***analysis of the study treatment safety and tolerability (Safety population)***, as all AEs identified after the study drug administration will be recorded.

Full Analysis Set This sample will consist of all enrolled patients, except for those who met at least one of the following criteria:

- 1) non-compliance with inclusion/exclusion criteria;
- 2) patient failing to take any dose of the study drug;
- 3) lack of any data on the subject after the study drug administration.

This was the best set for the Intention-to-treat method, so it will be used in the ***Intention-to-treat efficacy analysis (ITT-analysis) of the study therapy.***

Per Protocol set. This set will comprise all the subjects receiving per protocol therapy in full and completing all the scheduled visits. This set will be used for ***efficacy Per Protocol analysis.*** *Per Protocol set* will not include the subjects whose data are fully or partially invalid for analysis due to a protocol deviation.

The list of deviations which may result in complete or partial invalidity of data is developed by a medical expert jointly with a biostatistician according to the study design.

Protocol deviations resulting in full or partial data invalidity:

1. Violation of visit schedule.
2. Inappropriate distribution/issue of the study drug.
3. Prescription of prohibited therapy.
4. $\geq 25\%$ increase or reduction in the amount of the study therapy administered.
5. Inability to assess the subject's compliance using the formula (e.g. loss of pack with the product).
6. Major discrepancies between source documents and CRF detected during monitoring or another authorized check.
7. Violation of the procedure for obtaining Informed consent.
8. Non-compliance with the clinical study protocol procedures.
9. Inability to collect all subject's data used for evaluation of the study endpoints (e.g. lack of entries in source documents required for verification of inclusion/exclusion criteria, safety and efficacy criteria).

10. Other protocol deviations resulting in full or partial data invalidity.

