Based on the subject's age the study may use various versions of ADHD-RS-V. The following is suggested to monitor the scale impact on the results (unless the manufacturer provides another method of result unification): in all statistical analysis associated with ADHD-RS-V (both as a dependent variable and as independent variable) the statistical model should consider the factor of the scale used (children/teenagers).

Data treatment and all statistical calculations under the protocol will be made using SAS-9.4 statistical software.²

Evaluation of sample size

The sample size was assessed in accordance with the following rules and assumptions:

1. Statistical assumptions

- 1.1 the power of statistical criteria "P=(1- β)" will be taken as being equal to 80% (probability of correct rejection of the null hypothesis is 0.8);
- 1.2 the probability of a type I error " α " will be allowed to be less than 5% (the probability of the erroneous acceptance of an alternative hypothesis was less than 0.05);
- 1.3 statistical criteria of intergroup comparisons will be two-sided unless otherwise specified;
- 1.4 calculation of sample size will be based on the assumptions on the expected effect declared in the primary efficacy endpoint of the protocol;
- 1.5 ratio between sample sizes in Prospekta and Placebo group will be 1:1;
- 1.6 statistical hypotheses - null and alternative hypotheses on the difference between test product and placebo under the dosing regimen used:
 - a) primary endpoint:

$$H_0: \Theta_1 - \Theta_2 = 0$$

$$H_a: \Theta_1 - \Theta_2 \neq 0$$

where Θ_1 is proportion of events in Prospekta group,

Θ_2 is proportion of events in Placebo group;

- 1.7 calculation of sample size for statistical criteria was made using the following formula:

$$n_2 = kn_1$$

$$n_1 = \frac{(z_{\alpha/2} + z_{\beta})^2 * (\Theta_1 * (1 - \Theta_1) + \Theta_2 * (1 - \Theta_2))}{\epsilon^2}$$

where n_1, n_2 is sample size of Prospekta and Placebo group, respectively,

² Holder of license: OOO "NPF "Materia Medica Holding", No. 70100045.

$\varepsilon = \Theta_1 - \Theta_2$ is expected differences between frequencies of events in Prospekta and Placebo group;

k – coefficient of sample ratio between Prospekta and Placebo (1:1);

$z_{\alpha/2}$ – tabular value of two-sided z-test for α ;

z_{β} – tabular value for one-sided z-test for β .

1.8 final sample size will be determined using the formula:

$$N_T = N_{PP} / (1 - R_w)$$

where N_T – final sample size;

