N_{PP} – result of calculation in cl. 1.7 – cl.1.8, i.e. scheduled number of subjects completing the study per protocol;

R_w – withdrawal rate.

A priori estimates for parameter variables in the groups:

Primary endpoint:

Proportion of subjects with an event in Prospekta group will be at least 66%, proportion of subjects in Placebo group will be no more than 50%³.

Therefore based on cl. 1.7, 146 subjects per group will be needed. Given withdrawal rate ($R_w=0.2$) and based on cl. 1.8, 366 subjects will be needed ($n=183$ per group).

Statistical criteria

All statistical calculations will be made using two groups of statistical criteria:

- parametric - to obtain effective estimates for random parameters in case the relevant conditions of method/model applicability are not violated (e.g. sphericity, normality, risk proportionality, etc.)
- nonparametric – in all other cases.

Parametric criteria

The application of parametric criteria will be accompanied by a check of models for applicability (e.g. Kolmogorov-Smirnov test, Shapiro-Wilk test, etc.).

The following parametric methods and approaches are supposed to be used:

1. To evaluate the differences in continuous variables obtained in one group at two different visits – Student t-test for paired samples.
2. To assess the dynamics of the compared values – analysis of variance (ANOVA) or covariance (ANCOVA) in the modification with repeated measures.
3. In case of multiple comparisons between the groups variety of corrections for multiplicity will be used (Dunnett, Tukey, Scheffe, Holm adaptive test), etc.

³ Based on TD1061511-01.18.P study.

4. Generalized Linear Models and/or Mixed Linear Models will be used in case of abnormal data distribution.
5. Selection of the type of distribution, specification of factor and covariance structures of the model will be made using fit-statistics such as AIC (Akaike information criterion).

The following SAS software programs are supposed to be applied to the above listed tests and techniques:

- UNIVARIATE – normality verification of the distributions under comparison
- CORR, MEANS – calculation of descriptive statistics
- TTEST – Student's test with all modifications
- GLM – analysis of Generalized Linear Models for studying temporal dynamics (ANOVA, ANCOVA)
- GENMOD – analysis of Generalized Linear Models
- MIXED – analysis of Mixed Linear Models.

Non-parametric criteria

Below are potential types of comparisons with relevant criteria:

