1. To assess the dynamics of the compared indicators – Friedman test, non-parametric analogue of analysis of variance with repeated measures.
2. For frequency analysis of contingency tables $2 \times 2 - \chi^2$ (if the frequency under comparison > 5) or exact Fisher's test (if one of the frequencies under comparison < 5).
3. Cochran-Mantel-Haenszel test (modified χ^2 test for multiple comparisons) – to perform frequency analysis based on independent strata.
4. For frequency analysis of data on presence/absence of an event or outcome during repeated measurements (contingency tables with dependent strata) – survival analysis.

To perform the above-mentioned nonparametric statistical analysis the following SAS procedures are to be used:

- FREQ – Friedman test, χ^2 test and/or exact Fisher's test; Cochran-Mantel-Haenszel test.
- LIFETEST, PHREG – survival analysis.
- NPAR1WAY - Mann-Whitney U-test.

Safety parameters

Adverse events recorded during the study will be grouped into frequency tables by severity, seriousness and relationship with the study drug.

Data presentation

Descriptive statistics will be provided for each study continuous / interval variable. Numerical data will be presented by mean, standard deviation, min and max values. Comparisons

suggesting statistical conclusion will have the relevant confidence intervals. Outliers will be analyzed individually. The data will be grouped by visits. The categorical variables will be presented as frequency tables by visits.

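### Does the plan need changing because it ranks neither the ITT nor the Per Protocol analysis and lists multiplicity corrections that do little with two arms?

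*Combined protocol and SAP*

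**What the plan says.** Under Endpoints there is one primary endpoint: the proportion of children whose total ADHD-RS-V score falls by at least 25% after 8 weeks. Study design has two arms: "the patient is randomized to one of the two groups".

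The Samples section gives the FAS to the "Intention-to-treat efficacy analysis (ITT-analysis) of the study therapy" and the PP set to the "efficacy Per Protocol analysis". It does not call either one primary, supportive or a sensitivity analysis, and it has no rule for discordant results.

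Evaluation of sample size starts from the PP set. The formula's result is the "scheduled number of subjects completing the study per protocol", and Number of subjects plans 366 enrolled, "which is expected to yield at least 292 (146 in Prospekta and Placebo groups) patients completing all protocol procedures".

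Item 3 under Parametric criteria is the only clause on multiplicity: "In case of multiple comparisons between the groups variety of corrections for multiplicity will be used (Dunnett, Tukey, Scheffe, Holm adaptive test), etc". Item 2, directly above it, plans repeated-measures ANOVA or ANCOVA. The 2x2 and stratified tests that suit a binary endpoint are under Non-parametric criteria, items 2 and 3.

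For every analysis that involves ADHD-RS-V, the plan also says that "the statistical model should consider the factor of the scale used (children/teenagers").

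**The concern.** Three features together look like an opening for a choice made after unblinding.

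- Two efficacy analyses of the same endpoint are planned without a ranking. A reader who expects the FAS to decide finds that the sample size was worked out for PP completers, so the 80% power describes the PP test.
- The clause that might be expected to deal with multiplicity does not address this. It concerns comparisons between groups, and with two groups there is one such comparison per endpoint at a given visit. Only Holm could act across tests, and no family of hypotheses is named for it.
- The secondary endpoints are not expressly called supportive, and the Cochran-Mantel-Haenszel test is described as a multiple-comparison method although its stated use is stratified analysis.

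If either set could carry the claim, the 5% limit in cl. 1.2 would be exceeded. If the FAS decides, its power need not be 80%.

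**Working it through.** **Inputs from the plan.** Two-sided alpha 0.05, power 0.80, allocation 1:1 (cl. 1.1 to 1.5); responder rates 0.66 and 0.50; withdrawal 0.2; 183 per group enrolled.

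**The plan's own figure.** Cl. 1.7: n = (1.960 + 0.842)² × (0.66×0.34 + 0.50×0.50) / 0.16² = 7.849 × 0.4744 / 0.0256 = 145.4, so 146 per group. Cl. 1.8: 146 / 0.8 = 182.5, so 183 per group and 366 in total. Both reproduce.

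**Assumptions the plan does not supply.** All 183 per group enter the FAS, and a share s of them is in the PP set. Subjects outside the PP set respond (a) like completers, (b) at the placebo rate in both arms, or (c) are counted as non-responders. Each set is tested by two-sided chi-square at 5%. The results below come from binomial simulation.

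| Quantity | s = 0.8 (a / b / c) | s = 0.9 (a / b / c) |
|---|---|---|
| PP power | 80 / 80 / 80% | 84 / 84 / 84% |
| FAS power | 88 / 70 / 70% | 88 / 80 / 80% |
| Verdicts differ, planned effect | 11 / 14 / 15% | 6 / 8 / 8% |
| Either set significant, no drug effect | 7.3 / 7.3 / 6.8% | 6.7 / 6.7 / 6.5% |

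**Analytic check of the last row.** The PP set is nested in the FAS, so under (a) the two test statistics have correlation √s. For s = 0.8 that is 0.894, and the chance that at least one is significant is 7.1% two-sided, or 3.5% in the drug's favour against a nominal 2.5%. For s = 0.9 it is 6.5% two-sided.

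**Sample size if the FAS decides and the effect is diluted.** At s = 0.8 the FAS rates are 0.8×0.66 + 0.2×0.50 = 0.628 against 0.50 under (b), and 0.528 against 0.40 under (c). Cl. 1.7 then gives 232 and 235 per group. At s = 0.9 the rates are 0.644 against 0.50 and 0.594 against 0.45, which give 182 and 185, in line with the 183 planned. Under (a), 183 is more than enough.

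**Listed corrections.** With two groups and 290 degrees of freedom (2×146 − 2), the 5% critical values for t, Tukey and Scheffe are all 1.968. Dunnett with one active arm and one control is the same test. ADHD-RS-V is recorded at three visits, however, so the repeated-measures model in item 2 has 2×3 = 6 group-by-visit cells. For six means, taking 290 degrees of freedom as an illustration, Tukey's critical value is 2.87 and Scheffe's is √(5 × F(0.95; 5, 290)) = 3.35, against 1.97 unadjusted. There the corrections do work.

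**The case for a change.** The strongest case for a change is that a pre-specified plan should leave no room to choose the decisive result once data are unblinded, and that the remedy is one sentence. In roughly 1 trial in 7 to 9 at 20% exclusion, or 1 in 12 to 16 at 10%, the choice of set would change the verdict. PP membership is itself loosely bounded: the deviation list in the Samples section ends with a catch-all, and the text does not say that it closes before unblinding. Remarking that the FAS suits the ITT method does not make it decisive.

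The factual part of this stands: neither set is named. The step from there to a defect does not follow.

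- Error inflation needs a rule that success in either set counts. The plan contains no such rule.
- Inflating a completer target for withdrawal is routine. It does not make the PP set decisive, and the stated power is correct for the set it refers to.
- For a superiority hypothesis such as cl. 1.6, the FAS is the usual primary set, because PP membership depends on behaviour after randomisation. The plan lists the ITT analysis first.
- The opening section describes the document as a protocol summary, so its silence is weak evidence that no ranking exists.

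On the multiplicity clause, the complaint holds only for a single two-arm contrast at one visit. Striking Dunnett, Tukey and Scheffe would leave that contrast as it is and remove usable corrections for the repeated-measures contrasts. The clause also sits among the parametric methods, whereas the primary endpoint is binary, so the t critical values have no bearing on it.

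The remaining remarks are about wording. The endpoints are already labelled secondary, and hypotheses and sample size are stated for the primary endpoint alone. The label on the Cochran-Mantel-Haenszel test does not alter what the test does. The scale-version factor is already required.

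**Conclusion.** No change to the plan follows. The missing designation is a gap in detail that analysts of a two-arm superiority trial would normally fill by letting the FAS decide and reading the PP result beside it. No stated rule or number is wrong: 146 per group, 366 in total and 80% power for completers all reproduce.

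The size of the matter, assuming 10% to 20% of the FAS lies outside the PP set and all 183 per group enter the FAS, is as follows. The verdicts differ in about 6% to 15% of trials under the planned effect, and FAS power runs from about 70% to 88% depending on how many subjects are excluded and how they respond. A two-sided error of about 6.5% to 7.3% arises only if either set may carry the claim, which the plan does not allow for. The true gap between the sets is unknown. Some withdrawals, such as eligibility errors, would leave both sets, while protocol deviations could widen the difference.

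The multiplicity clause is harmless where it has no effect and useful where it has one.

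### No model or missing-data rule is tied to the ADHD-RS-V change endpoints, and the listed repeated-measures GLM, in its usual form, would drop children lacking a week-4 or week-8 score

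*Combined protocol and SAP*

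**What the plan says.** All references are to the combined protocol and SAP.

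- **Parametric criteria, item 2** gives the method for change over time: "analysis of variance (ANOVA) or covariance (ANCOVA) in the modification with repeated measures". The SAS list below it assigns this work: "GLM – analysis of Generalized Linear Models for studying temporal dynamics (ANOVA, ANCOVA"). The introduction to Statistical criteria names sphericity among the conditions to be checked, which fits classical repeated-measures ANOVA.
- **Item 4** gives the only stated trigger for mixed models: "Generalized Linear Models and/or Mixed Linear Models will be used in case of abnormal data distribution".
- **Item 5** adds that "specification of factor and covariance structures of the model will be made using fit-statistics such as AIC (Akaike information criterion"), and the SAS list includes "MIXED – analysis of Mixed Linear Models".
- The list is introduced tentatively ("The following parametric methods and approaches are supposed to be used") and assigns no method to any endpoint.
- **Non-parametric criteria, item 1** gives the Friedman test as the fallback for change over time.
- **Endpoints**: secondary endpoints 1-3 are changes from baseline at week 8 in the ADHD-RS-V total and its two subscales. Under the Schedule of study procedures the scale is completed at Visits 1, 2 and 3 only.
- **Samples**: the Full Analysis Set, used for ITT, excludes a child for missing data only if nothing at all was recorded after dosing. No imputation or other missing-data rule appears anywhere.

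**The concern.** The Full Analysis Set admits children with partial follow-up, but the procedure listed for change over time cannot use them in its standard form. PROC GLM with a REPEATED statement takes one row per child and discards the row if any repeated value is missing. With no missing-data rule, the software default would decide who is analysed.

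Item 4 makes this more likely. If the scores look normal, the plan gives no reason to move to PROC MIXED, although MIXED is the listed procedure that keeps children with incomplete visits. Non-normality is a reason to consider a generalized linear model; it is not a reason to choose a linear mixed model.

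At stake is whether the ITT result for three secondary endpoints describes the children in the Full Analysis Set or mainly those who completed. The trial prohibits ADHD drugs and withdraws children who need them, so dropout linked to poor response, and unequal between arms, is plausible.

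**Working it through.** **1. The plan's own figures.** Inputs from Evaluation of sample size: 66% v 50%, two-sided alpha 0.05, power 80%, R_w = 0.2.

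n = (1.960 + 0.842)² × (0.66×0.34 + 0.50×0.50) / 0.16² = 145.45, so 146 per group. Then 146/0.8 = 182.5, so 183 per group and 366 in total. Both figures reproduce. They rest on the binary primary endpoint, so nothing below changes them.

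**2. Which children are exposed.** Baseline ADHD-RS-V is needed for entry and the phone visits carry no score, so only Visit 2 (week 4) and Visit 3 (week 8) matter. The layout decides the rest:

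| Analysis | Only week 4 missing | Week 8 missing, week 4 present |
|---|---|---|
| GLM, one row per child, repeated visits | child dropped | child dropped |
| GLM ANCOVA of week 8 alone | child kept | child dropped |
| GLM, one row per visit | only that record lost | only that record lost |
| MIXED, one row per visit | only that record lost | only that record lost |

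**3. How many.** 366 × 0.2 = 73 lost and 366 × 0.8 = 293 kept, close to the 292 completers expected under Number of subjects. The plan defines R_w by per-protocol completion, so on that definition a child who missed Visit 2 is already among the 73. If instead 20% lack week 8 and a further 2%, 5% or 10% of week-8 attenders (assumed) miss week 4, the one-row-per-child GLM keeps 287, 278 or 264. Of the dropped children, 6, 15 or 29 would then have the week-8 score that the endpoint needs.

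**4. Precision.** Suppose 20% lack week 8 and all of them were seen at week 4. The variance of the week-8 effect using week-4 data, relative to complete cases, is (1 − r²) + 0.8r². For an assumed correlation r of 0.5 this is 0.75 + 0.20 = 0.95; for r = 0.8 it is 0.36 + 0.512 = 0.87.

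**5. Bias.** The documents give no SD, effect or visit correlation for these endpoints, so all values here are assumed. Simulation: 183 per arm, 2,000 trials, SD 8, true week-8 difference −2.0 and 60% of it at week 4, every leaver seen at week 4. Active children leave at random (logit −1.4). Placebo children leave with logit −1.6 + s × standardised week-4 score, where a higher score is a worse response. The estimate using week 4 regresses week 8 on week 4 within each arm and predicts at the mean for all children in that arm.

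| s | r | Missing | Complete cases | Using week 4 | Complete-case shortfall |
|---|---|---|---|---|---|
| 0 | 0.5 | 18.3% | −1.98 | −1.99 | about none |
| 0 | 0.7 | 18.3% | −2.02 | −2.01 | about none |
| 0.5 | 0.5 | 18.9% | −1.64 | −1.99 | 18% |
| 0.5 | 0.7 | 18.9% | −1.48 | −1.96 | 26% |
| 1.0 | 0.5 | 20.3% | −1.26 | −1.98 | 37% |
| 1.0 | 0.7 | 20.2% | −0.97 | −1.96 | 52% |

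Further simulations assumed SD 9, a true difference of 3, r of 0.5-0.7, about 20% dropout and every leaver seen at week 4. The estimate using week 4 stayed at about 3.0. Complete-case results were:

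- random dropout: 2.96-2.98;
- the same score-driven mechanism in both arms: between 2.99 and 2.6, depending on how the rule is specified (shortfall 0 to (3 − 2.6)/3 = 13%);
- score-driven dropout in placebo only: 1.0-1.6 in one set and 1.64 in another. The last is (3 − 1.64)/3 = 45% short and the lowest is 67% short.

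The placebo-only result shrinks when fewer leavers reach week 4. In one specification complete cases gave 1.40 when all leavers had a week-4 score, 2.07 when half did and 2.50 when a quarter did (53%, 31% and 17% short). These simulations compare week-8 complete cases with an estimate using week 4; they do not measure the loss of children who missed only Visit 2.

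**The case against.** A reader might infer that the plan deletes from the ITT analysis any child who misses a visit. The documents do not say that, and several points tell against it.

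- **Deletion is inferred.** The list is tentative, no procedure is assigned to endpoints 1-3, MIXED is available, and choosing covariance structures by AIC (item 5) points toward mixed-type modelling. This stands: deletion is the likely software default and not a rule of the plan. The same points confirm that the plan commits to no model.
- **Missing one visit is too broad.** Phone visits carry no score, and a week-8 ANCOVA would keep a child who missed only week 4. This stands.
- **73 overstates what can be recovered.** R_w counts failure to complete per protocol. The withdrawal criteria include screening failure and eligibility error, and ineligible children are outside the Full Analysis Set under any model. A child who leaves before week 4 has no post-baseline score, so a mixed model cannot use that child either. This stands; the net gain is below 73 by an unknown amount.
- **The large bias needs an adverse mechanism.** It requires score-driven dropout that differs by arm, which no passage predicts. This stands as a limit on size. It is not a reason to leave the method open.
- **The document calls itself a protocol summary**, so endpoint-level models may exist elsewhere. That is possible but cannot be checked here.

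**Conclusion.** The point holds in a limited form. Secondary endpoints 1-3 have neither a named model nor a missing-data rule. The method listed for change over time would, in its standard layout, drop Full Analysis Set children who lack a week-4 or week-8 score, and the stated trigger for mixed models is the wrong one.

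The loss is at most about 73 of 366 at the planned 20% withdrawal, with fewer recoverable. On assumed inputs the complete-case bias is nil under random dropout, roughly 0-13% when one score-driven mechanism acts in both arms, and about 45% or more in the most adverse scenario. The precision gain from using week 4 is modest, a variance ratio of 0.95 to 0.87. The bias figures assume that dropout depends only on arm and the observed week-4 score; the documents neither support nor exclude any one mechanism. The change should be made, but it concerns secondary endpoints only: the primary endpoint is a responder proportion and the sample size is unaffected.

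**What to change.** For secondary endpoints 1-3:

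- Name PROC MIXED as the main analysis, whatever a normality test shows, including every Full Analysis Set child with at least one post-baseline ADHD-RS-V score.
- Fit baseline score, scale version (which the plan already requires in every ADHD-RS-V analysis), arm, visit and arm-by-visit, with unstructured covariance. With two post-baseline visits that is three covariance parameters (two variances and one covariance). Report the week-8 arm contrast.
- Remove GLM repeated measures for these endpoints, and remove mixed linear models from item 4 as a remedy for non-normality.
- State the missing-at-random assumption and specify a sensitivity analysis that departs from it.

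The cost is mainly wording, since the procedure is already listed, plus slightly more analysis work. The downside is reliance on missing at random, which cannot be verified from the data but is weaker than what listwise deletion needs.
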